- To compare neonatal and maternal outcomes for women who transfer from home, freestanding midwifery units and alongside midwifery units, during or immediately after labour, with outcomes for women who are not transferred.
- To determine whether indication for transfer, time from decision making until transfer, duration of transfer or events after transfer are associated with poor outcomes for women who are transferred during or immediately after labour.

Methods

Study design

Prospective cohort study with planned place of birth as the exposure and neonatal mortality and morbidity as the primary outcome.

**Note: All comparisons between women who planned to give birth at home or in a midwifery unit and women who planned to give birth in an obstetric unit will be made using planned births in obstetric units as the reference group. This will maximise statistical efficiency and does not imply obstetric units are being considered the standard of care.*

Definitions

Planned birth at home

A birth which occurs for a woman who, at the start of care in labour, intended to give birth at home and who received care from a midwife during established labour at home, regardless of where the woman actually gives birth.

Planned birth in a midwifery unit (freestanding or alongside)

A birth which occurs for a woman who, at the start of care in labour, intended to give birth in a midwifery unit and who received care from a midwife during established labour in a midwifery unit, regardless of where the woman actually gives birth.

Planned birth in an obstetric unit

A birth which occurs for a woman who, at the start of care in labour, intended to give birth in an obstetric unit and who was admitted and received care during established labour in an obstetric unit.

Inclusion criteria

Data will be collected for all women planning birth at home, in freestanding midwifery units and in alongside midwifery units who are attended by a midwife during labour, for any amount of time, in their planned place of birth.

Data will be collected for all women planning birth in an obstetric unit except:

- Women who have an elective caesarean section or any caesarean section before the onset of labour
- Women who present in labour before 36 completed weeks gestation
- Women with a multiple pregnancy

Data will not be collected for women who have an unintended birth at home.

Study sites

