The only personally identifying information that will be returned to the NPEU will be the woman's postcode. The post code will be used to generate an index of multiple deprivation score for each woman. A measure of deprivation is important because if it is related to planned place of birth and having an adverse outcome it could be an important confounding factor that should be controlled for in the analysis. An application will be submitted to the Patient Information and Advisory Group (PIAG) in order to gain permission to collect women's postcode without asking for their consent to participate in the study (23). If approval is not granted by PIAG women's postcode will not be collected.

The outcomes for women and their babies who are transferred from their planned place of birth during or after labour will also be collected. This is important as these births are more likely to be associated with adverse outcomes. When a woman is transferred, the attending midwife will ensure the data form goes with the woman and that remaining data items are completed. The process of collecting these data will rely on the participation of midwives and occasionally neonatologists. Working with LCMs and, for example, the supervisors of midwives and heads of midwifery, a system to validate maternal and neonatal outcomes collected in the Birthplace forms will be developed, implemented and assured in each Trust. This will build on existing risk management reporting systems.

Completed data collection forms will be sent by midwives collecting data to their LCM. In order to ensure data quality, LCMs will validate data content and completeness, checking the maternity case notes if necessary. Also, to ensure all planned home births are included, the LCM will compare the number of forms received with appropriate local records, including records of planned home births, delivery suite and theatre registers and records of transfers to obstetric care. The LCM will detach and retain the front page and send the rest of the data collection form to the data management company for double data entry. The front page of the data collection forms will be retained by the LCMs and will be stored in a locked filing cabinet for at least 5 years or, if longer, the duration of time specified by local NHS Trust R&D procedures. LCMs will liaise with the relevant R&D departments in their Trust to ensure secure storage of these data.

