The detailed analysis plan will be formally agreed by the Co-investigator Group, with input from the Advisory Group, before data collection starts. Initially, the outcomes and characteristics of the women who planned birth in each setting will be described. Odds ratios will be calculated to compare outcomes by planned place of birth using the obstetric unit women as the comparison group. All women will be analysed by the setting in which they first received care from a health professional during labour, if that was their planned place of birth. Appropriate referral and transfer is an important element of the quality of care received by women. It is therefore important to count women in the group where they planned to give birth, regardless of where the birth actually took place.

The primary outcome of neonatal mortality and morbidity, for women considered to be at 'low risk' of complications at labour onset, will be compared by planned place of birth. The criteria set out in the NICE Intrapartum Care Guidelines, which are due for publication in September 2007, will be used to assess whether a woman would be defined as "low risk" at the onset of labour (30). Crude odds ratios will be calculated, each with a 95% confidence interval. Outcomes for each group (home, freestanding midwifery unit and alongside midwifery unit) will be compared with outcomes for women planning birth in an obstetric unit. These crude odds ratios will be adjusted in a regression model, to take account of potential confounders such as parity, age, deprivation score and other factors which may be associated with planned place of birth and adverse outcomes in pregnancy.

The secondary outcomes will be analysed in the same way as the primary outcome. Odds ratios calculated for the secondary outcomes will be presented with 99% confidence intervals. Since a large number of comparisons will be made it is important to use wider confidence intervals to reduce the likelihood of finding statistically significant associations by chance.

Crude odds ratios will be calculated comparing outcomes for women who transferred from each setting to the women who did not transfer from that setting, with 99% confidence intervals. These crude odds ratios will be adjusted in a regression model, to take account of potential confounders such as parity, age, deprivation score and other factors which may be associated with planned place of birth and adverse outcomes in pregnancy.

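### The group definitions require care in established labour, but the inclusion and analysis rules require only care in labour, so a woman transferred early from home or a midwifery unit is counted under two rules and belongs to no group under the third

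*Protocol*

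**What the plan says.** Planned place of birth is the exposure in this cohort, and the protocol assigns women to it in three places.

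- **Methods, Definitions.** A planned home birth is one for a woman who "intended to give birth at home and who received care from a midwife during established labour at home". For midwifery units she must have "received care from a midwife during established labour in a midwifery unit". The obstetric-unit definition covers a woman "who was admitted and received care during established labour in an obstetric unit". All three also require that she intended that setting when care in labour began.
- **Methods, Inclusion criteria.** For home and both types of midwifery unit, data are collected on women "who are attended by a midwife during labour, for any amount of time, in their planned place of birth". The obstetric-unit entry lists three exclusions and has no established-labour condition.
- **Analysis.** All women are to be "analysed by the setting in which they first received care from a health professional during labour, if that was their planned place of birth". The stated reason is that it is important to "count women in the group where they planned to give birth, regardless of where the birth actually took place".

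Under Tools and systems for data collection, the protocol says of births transferred from the planned setting: "This is important as these births are more likely to be associated with adverse outcomes". The protocol text at hand neither defines established labour nor says which of the three rules governs.

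**The concern.** The definitions describe a narrower population than the other two rules. The women in dispute are those seen in early labour at home or in a midwifery unit and moved before labour is established. Whether they count depends on which section the form designer, the local midwife or the analyst follows.

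This matters because the disputed women are all transfers, which the protocol itself links to worse outcomes. Leaving some of them out of the home and midwifery-unit groups could make those settings look safer in the primary comparison. It would also remove women from the secondary objectives on transfer.

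**Working it through.** **1. The rules applied to the same women**

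| Woman | Definitions | Inclusion criteria | Analysis rule |
|---|---|---|---|
| Planned home or midwifery unit, attended there in early labour, transferred before labour is established | No group: no established-labour care in the planned place, and no intention of an obstetric-unit birth when care began | Included | Home or midwifery unit |
| Planned obstetric unit, early problem, later establishes labour there | Obstetric unit | Included | Obstetric unit |
| Planned obstetric unit, delivered there in labour before it is established | No group | Included, unless one of the three listed exclusions applies | Obstetric unit |

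Rows 1 and 3 show the conflict. Rows 1 and 2 show the imbalance: under the definitions, a woman who establishes labour only after moving is lost, while her obstetric-unit counterpart is kept. Row 3 shows that the obstetric-unit group can lose women too.

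**2. Possible bias (sensitivity calculation)**

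Inputs from Sample size considerations: obstetric-unit rate 3.6 per 1,000; 20,000 obstetric-unit women, 17,000 home, 5,000 in each type of midwifery unit. Two inputs are assumptions because the protocol gives neither: f, the share of attended home or midwifery-unit women dropped by the definitions, and r, their risk relative to the women who remain.

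Set the home or midwifery-unit rate under the broad rule to 3.6 per 1,000, so that the true odds ratio is 1, and let the obstetric-unit group lose nobody. Then

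rate under the definitions = 3.6 / (1 − f + f × r).

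| f | r | Rate per 1,000 | Odds ratio |
|---|---|---|---|
| any | 1 | 3.60 | 1.00 |
| 2% | 2 | 3.6/1.02 = 3.53 | 0.98 |
| 5% | 3 | 3.6/1.10 = 3.27 | 0.91 |
| 10% | 3 | 3.6/1.20 = 3.00 | 0.83 |
| 10% | 4 | 3.6/1.30 = 2.77 | 0.77 |

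Any similar loss of higher-risk women from the obstetric-unit group would bring these values closer to 1.

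**3. Effect on power**

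The protocol's powers reproduce with the continuity-corrected two-proportion formula, two-sided 5% (sidedness is assumed): home increase 82.4% (stated 82%), home decrease 79.7% (80%), midwifery-unit increase 80.5% (80%), midwifery-unit decrease 80.1% (80%).

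For the before-and-after comparison I used the uncorrected form, power = Φ[(|p1 − p2| − 1.96 × SE0)/SE1], with SE0 from the pooled proportion and SE1 from the separate proportions. At f = 10% the home group falls to 17,000 × 0.90 = 15,300 and each midwifery-unit group to 5,000 × 0.90 = 4,500.

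| Comparison | All counted | 10% dropped |
|---|---|---|
| Home, 3.6 to 5.7 | 84.3% | 82.4% |
| Home, 3.6 to 2.0 | 82.4% | 79.9% |
| Midwifery unit, 3.6 to 6.8 | 83.1% | 80.4% |
| Midwifery unit, 3.6 to 1.2 | 85.0% | 81.0% |

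The largest fall is 4 percentage points. The issue is bias, not precision.

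**The case against.** The best defence is that the sections do different jobs: the inclusion criteria say whose data are collected, the definitions then classify, and the reference to any amount of time concerns duration, not stage of labour. The Analysis rule is itself conditional on the setting being the planned place. This reading is possible for the inclusion criteria. It does not dispose of the Analysis section, which is also a classification rule, covers all women and has no established-labour condition.

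Three other points stand in part.

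- Requiring established labour everywhere is a defensible design, since it gives a common starting point. The protocol does not adopt it consistently, and it sits badly with the stated aim of counting women where they planned to give birth.
- The wider collection rule means early transfers should be captured, and the detailed analysis plan, due before data collection starts, could settle the matter. So the problem can be repaired, but the protocol's own rules still conflict.
- The primary comparison is limited to women at low risk at labour onset. Some early transfers, moved for a risk factor already present, might be left out under any rule.

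A reader might infer that the loss is wholly one-sided. It is not: the obstetric-unit definition has the same condition, so a woman delivered there before established labour fails it too. A reader might also infer that the women lost are the highest-risk in their group. The protocol says only that transferred births are more likely to have adverse outcomes; it does not single out transfers before established labour.

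**Conclusion.** The inconsistency is real and lies in the exposure definition for the primary comparison. Under the definitions, early transfers from home or a midwifery unit belong to no group; under the inclusion and analysis rules they are counted where they planned to give birth.

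The direction of bias is conditional. If early transfers share the raised risk that the protocol attributes to transfers in general, applying the definitions favours home and midwifery units. If their risk is the same as that of other women, there is no bias.

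The size cannot be derived from the protocol. The illustrative range runs from an odds ratio of 1.0 to 0.77 when the truth is 1, and the lower end needs 10% of women dropped at four times the risk. It is tempting to scale from the 43% transfer figure under Birth at Home, but that is an upper figure for all transfers in labour and says nothing about how many happen before labour is established.

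**What to change.** State one assignment rule and use it identically in the Definitions, Inclusion criteria and Analysis for all four settings. The simplest course is to align the three definitions with the two broader rules already in the protocol: a woman belongs to the setting she intended when care in labour began, provided she was attended there in labour, however briefly. Then define established labour and report the analysis restricted to women who received care in established labour in the planned setting as a sensitivity analysis.

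The cost is the wording of three definitions and an instruction on the data collection form before collection starts. The core data list names transfer data without detail, so the form should be checked to confirm that it records whether labour was established in the planned setting; the sensitivity analysis needs that item. The small downside is that some brief early-labour attendances will be counted in each setting, including obstetric units, and the sensitivity analysis will show whether that matters.

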The national prospective cohort study described in this document is one component of the Birthplace Research Programme. The study aims to evaluate the safety of planned birth at home, in freestanding midwifery units, in alongside midwifery units and in obstetric units. Collecting information from all births planned at home in England represents a major challenge and it is acknowledged that there is no certainty this will be possible. Therefore, the Birthplace Feasibility Study, funded by the the Department of Health (DH) Policy Research Programme, is currently being conducted to evaluate the feasibility of the inclusion of the 'planned birth at home' component in this national prospective cohort study. A decision about whether or not feasibility has been demonstrated will be made in December 2007. If it is not feasible to collect information about planned birth at home, the national cohort study will only collect information on planned birth in midwifery units and obstetric units. If feasibility is demonstrated, the

planned birth at home component will be included in the cohort study to provide a complete picture of the outcomes associated with all the settings currently supported by the NHS for birth in England.

Aim

To compare the safety of planned birth at home, in freestanding and alongside midwifery units and in obstetric units in England.

Primary Objective

To compare neonatal mortality and morbidity for planned birth at home, in a freestanding midwifery unit and in an alongside midwifery unit with planned birth in an obstetric unit, for women judged to be at 'low risk' of complications at labour onset.*

Secondary Objectives

- To compare maternal morbidity for planned birth at home, in a freestanding midwifery unit and in an alongside midwifery unit with planned birth in an obstetric unit, for women judged to be at 'low risk' of complications at labour onset.
- To compare neonatal mortality and morbidity for planned birth at home, in a freestanding midwifery unit and in an alongside midwifery unit with planned birth in an obstetric unit, for all women, irrespective of risk at labour onset.
- To compare maternal and infant birth interventions and outcomes for planned birth at home, in a freestanding midwifery unit and in an alongside midwifery unit with planned birth in an obstetric unit, for women judged to be at 'low risk' of complications at labour onset.

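### Births before 36 weeks and multiple pregnancies are excluded from the obstetric-unit group only, so the secondary all-women comparison lacks a matching reference group

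*Protocol*

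**What the plan says.** The protocol's Inclusion criteria treat the settings differently.

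- **Home and both types of midwifery unit:** "Data will be collected for all women planning birth at home, in freestanding midwifery units and in alongside midwifery units", provided that a midwife gives care in labour, for however short a time, in the planned place. No gestation or plurality limit is given.
- **Obstetric units:** "Data will be collected for all women planning birth in an obstetric unit except" three categories. The first concerns mode of birth: "Women who have an elective caesarean section or any caesarean section before the onset of labour". The second concerns gestation: "Women who present in labour before 36 completed weeks gestation". The third concerns plurality: "Women with a multiple pregnancy".
- **Only other exclusion:** "Data will not be collected for women who have an unintended birth at home".

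The Secondary Objectives include a comparison of neonatal mortality and morbidity in each of the three other settings with obstetric units "for all women, irrespective of risk at labour onset". The Analysis section names parity, age and deprivation score as potential confounders and leaves other factors open. It does not mention gestation or plurality. No section applies the obstetric-unit exclusions to the other settings for this objective.

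**The concern.** An all-women comparison needs the same population limits on both sides. Here a woman who begins labour at 34 weeks and is cared for by a midwife at home as planned counts in the home group, even if she is then transferred. A woman at the same gestation who planned an obstetric-unit birth is never recorded. The same holds for twins.

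Any excess of adverse neonatal outcomes in these births would be attributed to planned setting. The data for the missing reference women are not collected, so no later analysis can restore them.

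A note under Outcomes has a related weakness. It interprets certain neonatal-unit admissions on the premise that the babies are mature, but the Inclusion criteria guarantee at least 36 weeks only for obstetric units.

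**Working it through.** **1. Which exclusions are asymmetric**

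| Exclusion | Obstetric unit | Home and midwifery units | Asymmetric? |
|---|---|---|---|
| Caesarean before labour | Excluded | Cannot enter: midwife care in labour is required | No |
| Labour before 36 completed weeks | Excluded | Not excluded | Yes |
| Multiple pregnancy | Excluded | Not excluded | Yes |

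The point rests on the last two rows.

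**2. Which analyses are exposed**

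There are five secondary objectives. Two are limited to low-risk women. The two on transfer make comparisons among home and midwifery-unit women and need no obstetric-unit match. That leaves the all-women neonatal objective. The primary objective is restricted to low-risk women by one external set of criteria applied in every setting. That restriction would be expected to remove these births, although the protocol does not reproduce the criteria.

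**3. The plan's own figures**

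The stated powers concern the low-risk comparison and do not depend on this point, but they were checked. The method is a two-proportion normal approximation with pooled null variance, continuity correction and a two-sided 5% level (two-sided is assumed).

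For home against obstetric unit, n₁ = 20,000, p₁ = 0.0036, n₂ = 17,000 and p₂ = 0.0057:

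- difference = 0.0021; correction = ½(1/20,000 + 1/17,000) = 0.000054
- pooled SE = 0.000703; unpooled SE = 0.000716
- z = (0.0021 − 0.000054 − 1.96 × 0.000703)/0.000716 ≈ 0.93, so power is 82.4% (stated 82%)

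The other five give 79.7%, 80.5%, 80.1%, 79.8% and 81.0%, against stated values of 80%, 80%, 80%, 80% and 81%. All six reproduce.

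**4. Why adjustment does not help**

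The obstetric-unit group has no women before 36 weeks and none with a multiple pregnancy. A model with terms for gestation and plurality would have to extrapolate the reference risk in those strata, because it has no data there to estimate it.

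**5. Size of the component**

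Inputs:

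- baseline of 3.6 per 1,000 (Sample size considerations; a low-risk figure, used here for illustration)
- f, the share of home or midwifery-unit births that are before 36 weeks or multiple (assumed)
- r, their relative risk of the composite outcome (assumed)

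The protocol gives neither f nor r. With no true effect of setting:

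rate outside obstetric units = 3.6 × [(1 − f) + f × r] per 1,000

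Example: f = 1% and r = 10 gives 3.6 × (0.99 + 0.10) = 3.92 per 1,000.

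Spurious odds ratios against obstetric units:

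| f | r = 2 | r = 5 | r = 10 |
|---|---|---|---|
| 0.2% | 1.002 | 1.008 | 1.018 |
| 0.5% | 1.005 | 1.020 | 1.045 |
| 1% | 1.010 | 1.040 | 1.090 |
| 2% | 1.020 | 1.080 | 1.181 |

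**6. In proportion to the study's precision**

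At 3.6 per 1,000, 17,000 home births give about 61 events, 5,000 births in one midwifery-unit type give 18, and 30,000 obstetric-unit births give 108.

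- At f = 1% and r = 5, the excess is 0.04 × 61 ≈ 2.4 events at home and 0.04 × 18 ≈ 0.7 in each midwifery-unit type.
- At f = 1% and r = 10, the home excess is 0.09 × 61 ≈ 5.5 events.
- The 95% confidence limits lie a factor of exp(1.96 × √(1/61 + 1/108)) ≈ 1.37 from the estimate for home, and exp(1.96 × √(1/18 + 1/108)) ≈ 1.65 for each midwifery-unit type.

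**The case against.** The strongest reply is that the Inclusion criteria govern data collection and do not define an analysis set. Broad collection in home and midwifery units loses nothing, because women can be dropped later, and it fits the stated aim (Study sites) of covering every planned home birth under NHS care. The detailed analysis plan is to be agreed before data collection starts and could make the restriction. This stands as an argument about where to put the fix. It does not remove the mismatch: the protocol sets an all-women objective against a reference group that is not all women, and plurality is not listed separately among the core data items a later restriction would need.

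A second reply is that such births will be few, since the protocol's background describes midwifery units as serving women at low risk. This bears on size and largely stands. It does not make the number zero, because the all-women objective itself presupposes higher-risk women in these groups.

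A reader might infer three stronger things that the document does not support.

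- **That the primary comparison is biased.** It is limited to low-risk women by common criteria, and nothing shows that these births survive that restriction.
- **That the all-women comparison is biased on balance against home and midwifery units.** About 10,000 of the 30,000 planned obstetric-unit women are not low risk and stay in the reference group. If they carried twice the risk (an assumption), the reference rate would rise by a factor of 2/3 + (1/3 × 2) = 1.33. That works in the opposite direction and exceeds every value in the table, although higher-risk women in the other settings would offset some of it. Only one component of bias is shown here, not the net bias.
- **That the inflation is 4% to 18%.** That range takes only f of 1% to 2% and r of 5 to 10. Smaller shares and risks are just as compatible with the document and bring the effect close to nil. A uniformly high r is also unsupported for a composite that includes birth injuries and meconium aspiration.

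**Conclusion.** The point holds for one secondary objective. As written, the all-women comparison sets groups that may contain births before 36 weeks and multiple pregnancies against a reference group that by design contains neither, and adjustment cannot repair this. If these births carry higher risk, this component runs against home and midwifery units. Its size cannot be known from the document. Over f = 0.2% to 2% and r = 2 to 10 the spurious odds ratio is about 1.00 to 1.18, and it is probably towards the lower end because few such births would be expected. The pre-labour caesarean exception is no part of the problem. The primary comparison is not shown to be affected, and the stated powers are untouched. Severity is moderate to minor: worth correcting before data collection starts, but no threat to the study's main conclusion.

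**What to change.** - Leave the collection criteria for home and midwifery units as they are. Adding the exclusions there would stop data being collected on the very women who should be described.
- Define the analysis set for the all-women comparison with obstetric units as singleton pregnancies with labour at 36 or more completed weeks, in all four settings.
- Record plurality explicitly on the data collection form. Gestation at delivery is already a core item.
- Report the excluded home and midwifery-unit births descriptively, by setting.
- Relabel the objective to match: all singleton women at 36 or more weeks, irrespective of other risk.

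The cost is one analysis-set definition, one data item and a small number of home and midwifery-unit women lost from one secondary comparison. The change removes this component entirely (spurious odds ratio 1.00). It does not make the comparison like for like in other respects: differences in case mix among the remaining higher-risk women still depend on adjustment.
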